10.2.2 Reporting of serious adverse events

All SAEs occurring after study start (i.e., signing of informed consent) up to 30 after DB study treatment discontinuation must be reported on AE pages in the eCRF and on an SAE form, regardless of the investigator-attributed causal relationship with study treatment or study-mandated procedures.

10.2.3 Follow-up of serious adverse events

Serious adverse events still ongoing at the EOS visit must be followed up until resolution or stabilization, or until the event outcome is provided, e.g., death.

10.2.4 After the 30-day follow-up period

New SAEs occurring after the 30-day follow-up period [consistent with the definition in Section 10.2.2] must be reported to the Actelion drug safety department within 24 h of the investigator's knowledge of the event, **only** if considered by the investigator to be causally related to previous exposure to the study treatment.

10.2.5 Reporting procedures

All SAEs must be reported by the investigator to the Actelion drug safety department within 24 h of the investigator's first knowledge of the event.

All SAEs must be recorded on an SAE form, irrespective of the study treatment received by the subject, and whether or not this event is considered by the investigator to be related to study treatment.

The SAE forms must be faxed to the Actelion drug safety department (contact details are provided on the SAE form). The investigator must complete the SAE form in English, and must assess the causal relationship of the event to study treatment.

Follow-up information about a previously reported SAE must also be reported within 24 h of receiving it. The Actelion drug safety department may contact the investigator to obtain further information.

If the subject is hospitalized in a hospital other than the study site, it is the investigator's responsibility to contact this hospital to obtain all SAE relevant information and documentation.

The reference safety document to assess expectedness of a suspect serious adverse reaction and reported by the sponsor to health authorities, IRBs/IECs, and investigators is the reference safety information section of the Investigator's Brochure [ACT-132577 IB].

Essential hypertension Protocol AC-080A201 Version 3 30 May 2016, page 81/112

Confidential

10.3 Pregnancy

If a woman becomes pregnant while on study treatment, study treatment must be discontinued. The investigator must counsel the subject and discuss the risks of continuing with the pregnancy and the possible effects on the fetus.

10.3.1 Reporting of pregnancy

Irrespective of the treatment received by the subject, any pregnancy occurring after study start (i.e., signing of informed consent) up to 1 month following study treatment discontinuation must be reported within 24 h of the investigator's knowledge of the event.

Pregnancies must be reported on the Actelion Pregnancy form, which is faxed to the Actelion drug safety department (see contact details provided on the Actelion Pregnancy form), and on a pregnancy page in the eCRF.

10.3.2 Follow-up of pregnancy

Any pregnancy must be followed to its conclusion and its outcome must be reported to the Actelion drug safety department.

Any AE and SAE associated with the pregnancy occurring during the follow-up period (up to 1 month) after study treatment discontinuation must be reported on the AE page in the eCRF. Any SAE occurring during the pregnancy must be reported on an SAE form as described in Section 10.3.1.

10.4 Study safety monitoring

Clinical study safety information (AEs, SAEs, laboratory values, ECGs, vital signs, and project-specific labs/examinations as required) is monitored and reviewed on a continuous basis by the Actelion Clinical Team (in charge of ensuring subjects' safety as well as data quality) by periodically monitoring clinical studies activities from protocol conception to database closure.

An ILSDRB (an external expert committee of hepatologists) provides ongoing assessment and advice regarding any hepatic event that may require further evaluation during the study.

Essential hypertension Protocol AC-080A201 Version 3 30 May 2016, page 82/112

Confidential

11 STATISTICAL METHODS

All statistical analyses will be conducted by Actelion or by designated CROs supervised by Actelion. A Statistical Analysis Plan (SAP) will provide full details of the analyses, data displays, and algorithms to be used for data derivations.

11.1 Analysis sets

11.1.1 Screened Analysis Set

This analysis set includes all subjects who were screened and received a subject number.

11.1.2 Full Analysis Set

The Full Analysis Set (FAS) includes all subjects randomized to a study treatment, who have a baseline mean trough SiDBP. Subjects are evaluated according to the study treatment they have been assigned to (which may be different from the study treatment they have received).

11.1.3 Per-Protocol Set

The Per-Protocol Set (PPS) includes all subjects from the FAS who have a mean trough SiDBP at Week 8 of Period II and do not have any major protocol deviations. Major protocol deviations will be described in the SAP. Subjects are evaluated according to the study treatment they have been assigned to.

11.1.4 Safety Set

The Safety Set includes all subjects who received at least one dose of study treatment in Period II. Subjects are evaluated according to the study treatment they have received.

11.1.5 Pharmacokinetic Set

The Pharmacokinetic (PK) Set includes all subjects from the PPS who had at least one evaluable PK trough sample.

11.1.6 Usage of the analysis sets

The primary efficacy analysis will be performed on the PPS based on treatment as randomized. Secondary and exploratory efficacy analyses will also be performed on the PPS. The FAS and PPS will be used for supportive and sensitivity analyses.

Safety analyses will be performed on the Safety Set based on treatment as treated.

Subject listings will be based on the Safety Set, unless otherwise specified. Subject disposition will be described for the Screened Analysis Set.

Pharmacokinetic analyses will be performed on the PK set.

Essential hypertension Protocol AC-080A201 Version 3 30 May 2016, page 83/112

Confidential

11.2 Variables

11.2.1 Primary efficacy variable(s)

The primary efficacy variable is the change from baseline to Week 8 of DB treatment period (Period II) in mean trough SiDBP, measured by OBPM.

11.2.2 Secondary efficacy variables

Secondary efficacy variables include (measured by OBPM, unless specified otherwise):

- Change from baseline to Week 8 of DB treatment period (Period II) in mean trough SiSBP;
- Control and response rates at Week 8 of DB treatment period (Period II) based on trough SiDBP [defined as in Section 6.1.2];
- Control and response rates at Week 8 of DB treatment period (Period II) based on trough SiSBP [defined as in Section 6.1.2];
- Change from baseline to Week 8 of DB treatment period (Period II) in 24-h mean DBP, measured by ABPM;
- Change from baseline to Week 8 of DB treatment period (Period II) in 24-h mean SBP, measured by ABPM;
- Trough to peak ratio for DBP based on ABPM.

11.2.3 Other efficacy variables

Other efficacy variables include:

- Changes from baseline to Week 2 and Week 4 of DB treatment period (Period II) in mean trough SiSBP and SiDBP (measured by OBPM);
- Change from baseline to Week 8 of DB treatment period (Period II) in mean day time ABPM;
- Change from baseline to Week 8 of DB treatment period (Period II) in mean night time ABPM;
- Trough to peak ratio for SBP based on ABPM;
- Changes from baseline to Week 2 of withdrawal period (Period III) in mean trough SiSBP and SiDBP (measured by OBPM);
- Changes from Week 8 of Period II to Week 2 of withdrawal period (Period III) in mean trough SiSBP and SiDBP (measured by OBPM).

11.2.4 Safety variables

Safety variables include:

- Treatment-emergent AEs;
- Adverse events leading to premature discontinuation of study treatment;

Essential hypertension Protocol AC-080A201 Version 3 30 May 2016, page 84/112

Confidential

- Treatment-emergent deaths;
- Treatment-emergent SAEs;
- Treatment-emergent ECG abnormalities;
- Treatment-emergent marked laboratory abnormalities [as defined in Appendix 1];
- Changes from baseline to Weeks 2, 4 and 8 of DB treatment period (Period II) in laboratory parameters;
- Changes from baseline to Week 4 and Week 8 of DB treatment period (Period II) in ECG parameters (PR, QRS, QT, QTcB, QTcF);
- Changes from baseline to Weeks 2, 4 and 8 of DB treatment Period (Period II) in body weight and HR.

Treatment-emergent is defined in Section 10.1.1.

11.2.5 Other variables

11.2.5.1 Pharmacokinetic variables

• plasma concentrations of ACT-132577 , measured at steady state at Weeks 2, 4 and 8 in DB treatment period (Period II).

11.2.5.2 Pharmacodynamic variables

Trough plasma concentrations of ET-1, measured at steady state at Weeks 2, 4 and 8 in DB treatment period (Period II)

11.3 Description of statistical analyses

11.3.1 Overall testing strategy

The primary analysis will be performed at a type I (false-positive) error of $\alpha = 0.05$ (two-sided) using 95% confidence intervals (CIs). Secondary efficacy variables will also be analyzed at $\alpha = 0.05$ (two-sided). Dunnett's test will be applied when comparing multiple doses of ACT-132577 versus placebo. The active comparator will be excluded from all statistical tests related to dose-response, but will be compared separately versus placebo.

Essential hypertension Protocol AC-080A201 Version 3 30 May 2016, page 85/112

Confidential

11.3.2 Analysis of the primary efficacy variable(s)

11.3.2.1 Hypotheses and statistical model

The null hypothesis to be tested is that there is no dose-response for the primary endpoint.

$$H_0$$
: $\mu_0 = \mu_1 = \mu_2 = \mu_3 = \mu_4$

Here, μ_i denotes the mean change from baseline to Week 8 in mean trough SiDBP (μ) for ACT-132577 dose (i) (where i = 0 corresponds to placebo). A value of $\mu_i < 0$ corresponds to a decrease in SiDBP.

The alternative hypothesis is that there is a monotonic dose-response for the primary endpoint.

H₁:
$$\mu_0 \ge \mu_1 \ge \mu_2 \ge \mu_3 \ge \mu_4$$
 and $\mu_i > \mu_j$ for at least one $i > j$ or $\mu_0 \le \mu_1 \le \mu_2 \le \mu_3 \le \mu_4$ and $\mu_i < \mu_j$ for at least one $i > j$

Note that larger values of μ_i –corresponding to less decrease (or more increase) from baseline to Week 8 in mean trough SiDBP with increasing dose of ACT-132577– are less favorable. The first part of the alternative hypothesis corresponds to ACT-132577 being superior to placebo, whereas the second part corresponds to ACT-132577 being worse than placebo.

11.3.2.2 Handling of missing data

In subjects without a post-baseline mean trough SiDBP the baseline will be carried forward (i.e., the change from baseline will be set to zero). In subjects without a post-baseline mean trough SiDBP obtained at Week 8, the last post-baseline measurement will be carried forward. Note there will be no missing data for the primary efficacy variable in the PPS.

[figure not shown]
11.3.2.3 Main analysis

The primary analysis will be conducted on the PPS.

The change from baseline to Week 8 of DB treatment period (Period II) in mean trough SiDBP will be analyzed using the MCP-Mod approach [Bretz 2005, Pinheiro 2006]. In brief, this consists of a set of Multiple Contrast Tests (MCTs) to establish the existence of a dose-response and a set of pre-specified dose-response models to describe the dose-response curve.

Some examples of dose response relationships are given in Figure 2 below, where it is assumed that the minimum response will be obtained with placebo (0 mg) and the maximum response (4–5 mmHg, placebo corrected) will be reached at the highest dose of ACT-132577 (50 mg).

Figure 2 Examples of dose-response relationships

Six candidate dose response models will be considered: linear, linear in log-dose, quadratic, E_{max} , sigmoidal E_{max} and logistic. The analysis will be performed using the R-package *DoseFinding* [Bornkamp 2015]. A dose-response relationship is demonstrated if at least one of the six MCTs has an adjusted p-value < 0.05. The best fitting model based on Akaike's Information Criterion will be used to estimate the minimum effective dose, defined as the dose that achieves a placebo-corrected mean reduction from baseline of at least 4 mmHg with a 95% CI excluding 0.

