11.5 Sample size

11.5.1 Sample size justification

In a previous study with macitentan in essential hypertension (AC-055-201) the within-group SD for the change from baseline to Week 8 in SiDBP was 7.4 mmHg (90% CI: 7.0–8.0). In the sample size calculations SDs of 7–9 mmHg are considered.

Essential hypertension Protocol AC-080A201 Version 3 30 May 2016, page 91/112

Confidential

It is assumed that the maximum difference versus placebo is achieved at the highest dose of ACT-132577. For the dose-response curves four scenarios were considered [see Figure 2]. These are, in fact, sigmoidal E_{max} curves.

For the sample size it was required that the power to demonstrate the existence of a dose-response relationship is 90% for each of the four scenarios. A total of 70 subjects per group in the PPS (i.e., 420 subjects in total) satisfied this condition and would also allow for sufficiently precise estimation of the dose-response curve. Assuming a drop-out rate of approximately 20%, a total of 90 patients per group would need to be randomized (i.e., 540 in total).

The power for the MCP-Mod approach to demonstrate the existence of a dose-response relationship with 70 subjects per group (PPS) is given in Table 2 for various combinations of placebo-corrected differences and SDs.

Table 2 Power to demonstrate a dose-response relationship with n = 70 per group (PPS)

	Scenario 1	Scenario 2	Scenario 3	Scenario 4
Delta*	4.9	4.5	4.5	4.0
SD				
7	99%	99%	99%	99%
8	99%	99%	99%	99%
9	98%	96%	98%	97%

^{*}Maximum difference versus placebo (mmHg) PPS = Per-Protocol Set

Conservatively assuming that the difference versus placebo is 4 mmHg and the SD is 9 mmHg, the power for the MCP-Mod approach is > 95% for the four scenarios considered.

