The null hypothesis of ‘no dose-response’ will be rejected if at least one of the six Multiple Contrast Tests (MCTs) has a multiplicity adjusted p-value < 0.05. All statistically significant models (i.e., with an adjusted p-value < 0.05) are fitted in the Mod step and for each model Akaike’s Information Criterion (AIC) is calculated. The smaller the value of AIC (= model deviance + 2 times the number of model parameters), the better the fit. The analysis will be performed using the R-package *DoseFinding* [Bornkamp 2016]. The basic R-code is:

```
library(DoseFinding)
doses <- c(0, 5, 10, 25, 50)
candMod <- Mods(linear = NULL, linlog = NULL, quadratic = -0.005, emax = 50,
               sigEmax = c(50, 0.5), logistic = c(50, 50), doses = doses,
               direction="decreasing")
MMfit <- MCPMod(dose=dose, resp=resp, data=DF, addCovars=~base, models =
candMod, Delta=3)
```

In the Mods function call the candidate models are specified, together with the assumed direction of the effect (decreasing for change from baseline in blood pressure). In the call to the MCPMod function, DF is a data frame with objects dose, resp (for response), and base (for the baseline value) and Delta is a target difference vs placebo (Delta=3 for DBP; Delta=5 for SBP). The object *MMfit* will be summarized to obtain the MCP test, parameter estimates, target dose and AIC. These elements will go in a summary table. The object will be plotted to display the fitted dose-response curves.

Subgroup analyses based on MCP-Mod can be performed by fitting the selected model by subgroup using the *fitMod* function for which the basic R-code is:

```
MMfit1 <- fitMod(dose=dose, resp=resp, data=DF[DF$subg==1,], addCovars=~base,
model=MMfit$selMod)
MMfit2 <- fitMod(dose=dose, resp=resp, data=DF[DF$subg==2,], addCovars=~base,
model=MMfit$selMod)
```

As a supportive analysis to MCP-Mod, change from baseline to Week 8 in DBP and SBP will also be analyzed in an ANCOVA model using the Dunnett test.

```
proc mixed data=dset;
  class treat;
  model outcome=treat base;
  lsmeans treat / adjust=Dunnett diff=control('0') cl;
  where week=8 and treat in (0,1,2,3,4);
run;
```

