10 STATISTICAL ANALYSES

10.1 Overall testing strategy

All statistical testing will be performed at a two-sided significance level of 0.05 using 95% confidence intervals (CIs).

In the main analysis of the primary endpoint in the PPS the type I error is controlled by the MCT part of the MCP-Mod methodology. The primary objective of the trial will be evaluated based on this analysis.

The type I error of the MCP-Mod analysis in the FAS is similarly protected. In the other supportive analysis of the primary endpoint Dunnett's test will be used to correct for testing multiple doses vs placebo. The alpha is formally controlled only for the main analysis; all other analyses are considered exploratory.

In all analyses of secondary and other efficacy variables, no correction will be made for multiple testing.

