10.6.3 Main analysis

The change from baseline to Week 8 of DB treatment period (Period II) in mean trough SiDBP will be analyzed using the MCP-Mod approach [Bretz 2005, Pinheiro 2006] described in Section 9.1.

A placebo-corrected mean reduction from baseline of at least 4 mmHg is considered clinically relevant.

Some examples of E_{\max} dose-response relationships are given in Figure 3, where it is assumed that the minimum response will be obtained with placebo (mean change from baseline -4 mmHg) and the maximum response (change from baseline -8 or -9 mmHg) will be reached at the highest dose of ACT-132577 (50 mg).

Figure 3 **Examples of E_{\max} dose-response relationships**

Six candidate dose-response models were pre-specified in the protocol: linear, linear in log-dose, quadratic, E_{\max} , sigmoidal E_{\max} and logistic. The analysis will be performed using the R-package *DoseFinding* [Bornkamp 2016]. A dose-response relationship is demonstrated if at least one of the six MCTs has an adjusted p-value < 0.05. The best fitting model will be selected based on AIC. That model will be used to estimate the minimum effective dose, defined as the dose that achieves a placebo-corrected mean reduction from baseline of at least 4 mmHg with a 95% CI excluding 0.

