13 LIST OF SUMMARY TABLES, LISTINGS AND FIGURES

The table, listing, and figure naming conventions have three components: **Display** (T, L, F), **Name** (free text, in general not more than eight characters, but if required to maintain uniqueness up to a maximum of ten characters), **Suffix** (for example, for analysis sets, or subgroups, not longer than four characters). Multiple suffixes can be added; components/suffixes are separated by ‘_’. Example: *T_TEAE_SAF, summary table (T) of treatment-emergent adverse events (TEAE) on the SAF.*

The mock layout column refers to the BST standard Outputs Version 3.0 as of March 31, 2016.

A number of outputs have been identified as key outputs based on which an initial assessment of the dose-response relationship can be made. These are indicated with a ‘Yes’ in the ‘Key’ columns of the tables below.

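### The best-fitting-model curve and the minimum-effective-dose rule use a 95% CI from one AIC-selected model, with no stated method and no allowance for the selection

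*Protocol*

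**What the plan says.** SAP 9.2 describes two steps. Six candidate shapes are tested by multiple contrasts; all models whose contrast is significant "are fitted in the Mod step and for each model" an AIC value is obtained. SAP 10.6.3 then states: "The best fitting model will be selected based on AIC. That model will be used to estimate the minimum effective dose". That dose must give a placebo-corrected fall of at least 4 mmHg, with a 95% CI that excludes zero. Protocol 11.3.2.3 has the same rule: the best-fitting model by Akaike's "Information Criterion will be used to estimate the minimum effective dose".

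SAP 13.6.1 lists a figure and a table for the best-fitting model (both named DBP_MCPMOD_SEL). The figure is marked as key, and SAP 13 explains that marking: "A number of outputs have been identified as key outputs based on which an initial assessment of the dose-response relationship can be made". The subgroup curves (SAP 9.2, 10.6.5) also refit only the selected model.

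SAP 10.1 sets the 95% level, but no section says how an interval on the fitted curve is calculated. Model averaging, bootstrapping or any other allowance for selection does not appear.

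**The concern.** A model picked because it fits these data best is then treated as if it had been fixed beforehand. Its ordinary interval leaves out the uncertainty about which model is right, and any misfit of the one chosen. With five dose groups, AIC's penalty favours two-parameter models, so a straight line or log-line can win when the truth is a sigmoid. Such a model draws a narrow band in the wrong place.

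This matters because the study exists to choose Phase 3 doses (Protocol 1.3, 3.2), and the re-estimation SAP (sections 1 and 3) gives precision of the curve and of the selected doses as an aim of the sizing. Intervals that overstate this precision at 10 and 25 mg work against that aim.

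**Working it through.** **Inputs**
- 70 per group in the PPS, five dose-response groups, lisinopril excluded (Protocol 11.5.1, SAP 9.2).
- SD 9, from Protocol 11.5.1: "Conservatively assuming that the difference versus placebo is 4 mmHg and the SD is 9 mmHg".
- Planning curves from the R code in the re-estimation SAP: sigmoidal Emax with ED50/ED90 of 12.5/25, 12.5/50, 25/50 and 25/75 mg. Maximum effects are 4.9/4.5/4.5/4.0 mmHg (Protocol Table 2; the code uses 5 for curve 1).
- Six candidate shapes and starting values from SAP Table 3; two-sided 0.05.
- Assumed, because the documents are silent: ED50 up to 75 mg, Hill 0.5-10, logistic scale 0.5-25, and delta-method intervals. No baseline covariate, so SD is residual.

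**True effects at 25 mg.** Hill h = ln 9 / ln(ED90/ED50), which gives 3.17, 1.58, 3.17 and 2.00. Effect(25) = max × F(25)/F(50), with F(d) = d^h/(ED50^h + d^h):
- Curve 1: 4.9 × 0.900/0.988 = 4.46
- Curve 2: 4.5 × 0.75/0.90 = 3.75
- Curve 3: 4.5 × 0.50/0.90 = 2.50
- Curve 4: 4.0 × 0.50/0.80 = 2.50 mmHg

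**The plan's own figure.** Protocol Table 4 gives 47, 63 and 79 per group for 80, 90 and 95% average power at SD 9. Simulation of the contrast test (critical value 2.17) gives 80.9, 90.2 and 95.2%, so the testing step is reproduced. Protocol Table 2 (98/96/98/97%) does not reproduce: the same test gives 98/92/94/87%. That is a separate matter and does not affect coverage.

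**Why a selected line misses.** Curve 1 has true effects 0, 0.26, 1.64, 4.46 and 4.90 at 0, 5, 10, 25 and 50 mg. Centred doses are -18, -13, -8, 7 and 32, with sum of squares 1630.
- Slope = 171.6/1630 = 0.105 per mg; fitted 25 mg effect = 2.63 against a true 4.46.
- Half-width = 1.967 × 25 × 9/√(70 × 1630) = 1.31, so the typical interval ends near 3.94, below the truth.
- The line reaches 4 mmHg at 38 mg; the curve does so near 20 mg.

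For a line or log-line, the effect at every dose is one slope times a constant. All doses share one t-statistic, so a CI that excludes zero at one dose excludes it at all of them.

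**Coverage of the nominal 95% CI in positive trials.** Three separately coded simulations were run (700, 5,000 and 1,500 trials per curve). The 10 mg column comes from the first and third, the last column from the second.

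| Curve | 25 mg, % | 10 mg, % | Line or log-line selected, % |
|---|---|---|---|
| 1 | 71, 69, 70 | 62, 64 | 49 |
| 2 | 78, 74, 82 | 52, 53 | 72 |
| 3 | 93, 92, 93 | 25, 31 | 80 |
| 4 | 92, 93, 93 | 74, 76 | 83 |

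The spread on curve 2 exceeds simulation error and presumably reflects details of the fitting. At 50 mg coverage is 95-97% (first simulation). The pairwise 25 mg CI covers 95-96% in the same trials, so the shortfall arises in the modelling step. Results at 25 mg are similar with SD 8 (70/71/94/92%), SD 7.4 (73/70/93/90%) and 63 per group (70/77/93/93%). The last is close to the 490 randomised in SAP 4.2 if 80% enter the PPS: 490 × 0.8/6 ≈ 65.

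**With selection repeated.** Parametric bootstrap, 500 trials × 300 resamples per curve, 25 mg effect:

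| Interval | Coverage, % (curves 1-4) | Median half-width, mmHg |
|---|---|---|
| Selected model's own | 69/74/92/93 | 2.4/2.3/1.3/1.3 |
| Bootstrap, AIC re-selected | 96.1/97.2/97.5/97.3 | 2.8-2.9 |
| Bootstrap, AIC-weighted average | 95.1/95.7/94.7/94.1 | 2.5 |

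These resamples chose or averaged over all six models without repeating the significance step. In the main simulation, dropping that step changed coverage by less than 1 point.

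**The case against.** Much of the case for leaving the plan alone is right, and it limits the point. A reader might infer four stronger conclusions.

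- **That the plan prescribes the selected model's own CI.** It does not; the method is unstated. The coverage figures depend on that reading.
- **That the whole dose-response estimate rests on one model.** SAP 9.2 plots every significant curve, and SAP 13.6.1 lists general MCP-Mod outputs besides the best-fitting-model ones. The ANCOVA/Dunnett by-dose table and figure are key outputs for PPS and FAS (SAP 13.6.2). None of these feeds the minimum effective dose, but whoever chooses doses will see them.
- **That the minimum effective dose would be wrong because of the CI.** The rule also needs an estimated 4 mmHg, and even the bootstrap half-width at 25 mg is below 4. Replacing the CI and keeping the selected estimate changed the minimum effective dose in 1/372, 5/288, 15/307 and 5/248 trials (0.3-5%).
- **That the failure is uniform.** At 25 mg the serious shortfall is confined to curves 1 and 2, and under curve 1 a line or log-line wins only about half the time.

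It is also fair that the objective is exploratory, that six models and an objective criterion are pre-specified, and that selection is not imprecise in itself. The selected estimate's RMSE at 25 mg (1.61/1.33/1.20/1.19 mmHg) is close to or below the pairwise standard error, 9 × √(2/70) = 1.52. Averaging lowers it to 1.31/1.09/1.11/1.11, but making averaging the main estimator is a trade-off rather than a correction. What remains is the interval: its method is unstated, and its obvious form does not have 95% coverage.

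**Conclusion.** The concern holds for the intervals. The best-fitting-model outputs and the CI in the minimum-effective-dose rule come from one AIC-selected model, with no method stated and no allowance for selection. On the natural reading, nominal 95% intervals cover the true placebo-corrected effect about 70-82% of the time at 25 mg under curves 1 and 2, about 92-93% under curves 3 and 4, and about 25-76% at 10 mg.

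These figures assume 70 per group, SD 9, positive trials, the fitting bounds listed above and no baseline covariate. The 25 mg result is stable over SD 7.4-9 and 63-70 per group; the 10 mg result was checked only at 70 per group and SD 9. The primary contrast test and its type I error are untouched. The documents do not support a claim that dose selection itself fails. The plan should be changed, but this does not threaten the primary conclusion.

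**What to change.** In Protocol 11.3.2.3 and SAP 9.2 and 10.6.3, keep the contrast test and the AIC-selected point estimate. State that every 95% CI for the fitted curve, the effects at the study doses and the minimum effective dose comes from a bootstrap that repeats the contrast test and AIC selection in each resample. Specify the parameter bounds, the number of resamples and the handling of resamples in which no contrast is significant. Add AIC-weighted averaging of the significant models as a sensitivity analysis.

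The cost is SAP wording and a short R loop, with no new data. The downside is wider reported intervals: at 25 mg a half-width of about 2.8-2.9 mmHg (2.5 with averaging) instead of 1.3-2.4. That is close to the pairwise 2.99, so much of the precision apparently gained from the model goes once selection is counted.

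When the code is edited, reconcile one related conflict: the SAP 9.2 call sets the target difference for DBP at 3 mmHg, while the minimum effective dose is defined at 4 mmHg.
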